7.1.3.6 Infusion-Related Reactions to Sym015

An IRR is defined as an AE occurring during the Sym015 infusion and up to 2 hours after the end of infusion (EOI), which is assessed by the Investigator to be related to the infusion of Sym015. Signs of IRRs may include but are not limited to facial flushing and swelling, shortness of breath, headache, diaphoresis, tachycardia, hypotension, chills, rigors, chest and throat tightness, as well as chest, back and/or abdominal discomfort.

7.1.3.7 Handling of Infusion-Related Reactions to Sym015

The risk of an IRR is highest for the first administration of a mAb and diminishes with subsequent infusions.

If an IRR occurs, it should be classified according to the Common Terminology Criteria for Adverse Events (Version 4.03) (CTCAE v4.03). Recommended management guidelines are shown in [Table 6](#). In all cases, the Investigator should use best clinical judgment in managing such reactions.

Table 6 Infusion-Related Reactions Management Guidelines

CTCAE Grade	Management/Treatment
Grade 1 Mild transient reaction; infusion interruption not indicated; intervention not indicated	
 Continue infusion; consider slowing to 50% of the prior rate Monitor closely If infusion is extended, administer subsequent infusions during Cycle 1 at the prolonged rate Thereafter, if vital signs remain stable and symptoms do not recur, at the discretion of the Investigator an attempt may be made to slowly increase the rate of infusion. Final infusion duration should not be briefer than the initial rate attempted in the patient
Grade 2 Therapy or infusion interruption indicated but responds promptly to symptomatic treatment (e.g., antihistamines, NSAIDs, narcotics, IV fluids); prophylactic medications indicated for ≤ 24 h	
 Interrupt infusion for a minimum of 30 minutes Administer symptomatic treatment (e.g., antihistamines, NSAIDs, etc.) and appropriate supportive care (e.g., bronchodilator, oxygen, etc.), as indicated When symptoms have resolved or decreased to Grade 1, restart infusion at 50% of the prior rate Monitor closely If symptoms recur, stop the infusion, institute remedial therapy, monitor closely and evaluate whether the patient can continue the trial Administer subsequent infusions during Cycle 1 at the prolonged rate Thereafter, if vital signs remain stable and symptoms do not recur, at the discretion of the Investigator an attempt may be made to slowly increase the rate of infusion. Final infusion duration should not be briefer than the initial rate attempted in the patient
Grade 3 Prolonged (e.g., not rapidly responsive to symptomatic medication and/or brief interruption of infusion); recurrence of symptoms following initial improvement; hospitalization indicated for clinical sequelae	
 Discontinue the infusion Administer symptomatic treatment (e.g., antihistamines, NSAIDs, glucocorticoid etc.) and appropriate supportive care (e.g., bronchodilator, oxygen, IV fluid etc.), as indicated Do not resume infusion Patient will either be discontinued from further treatment or receive subsequent treatments at a reduced dose; if treatment is continued administer subsequent infusions during Cycle 1 at 50% of the prior rate Thereafter, if vital signs remain stable and symptoms do not recur, at the discretion of the Investigator an attempt may be made to slowly increase the rate of infusion. Final infusion duration should not be briefer than the initial rate attempted in the patient
Grade 4 Life-threatening consequences; urgent intervention indicated	
 Discontinue infusion Administer necessary life-support measures, as indicated Discontinue from further treatment

Abbreviations (in alphabetical order): CTCAE, Common Terminology Criteria for Adverse Events v4.03; h, hours; IRR, infusion-related reaction; IV, intravenous; NSAID, nonsteroidal anti-inflammatory drug

7.1.4 Dose-Adjustment and Delays of Sym015

The dose of Sym015 in mg/kg assigned to the individual patient will be confirmed by the Sponsor or designee prior to C1/D1 on the Screening and Allocation Form.

Based on the body weight of the patient, the site will calculate the nominal dose of Sym015 to be administered in mg.

Weight changes ($> \pm 10\%$) for a patient during trial will require recalculation of the dose. Refer to Section [7.1.4.1](#).

Furthermore, dose-delays of Sym015 and intra-patient dose-reduction(s) may also be required upon occurrence of specific toxicities. Refer to Section [7.1.4.2](#).

7.1.4.1 Dose-Adjustment for Body Weight

Sym015 is dosed in mg/kg and the dose to be administered will be calculated based on the actual body weight of the patient. The dose calculated may be used for subsequent infusions, unless body weight changes of $\geq \pm 10\%$, in which case the dose should be adjusted according to the change in body weight. Recalculation for lower weight changes is allowed.

7.1.4.2 Dose-Delays for Sym015-Related or Disease-Related Toxicities

Clinical judgment will be used when determining whether it is advisable to continue a patient on to the next dosing. In order to dose a patient, the following criteria must be met:

- ANC $> 1.0 \times 10^9/L$ (1000/mm³)
- Platelet count $> 60 \times 10^9/L$ (60,000/mm³)
- Any ongoing AEs should NOT meet the criteria for DLT, during the DLT observation period
- Any ongoing AEs, assessed as possibly, probably, or related to Sym015, should have either ameliorated to \leq Grade 1 severity, returned to baseline status, or resolved with the exception of Grade 2 clinical events that are being adequately controlled with best supportive care (e.g., nausea, vomiting, diarrhea, fatigue) and asymptomatic laboratory abnormalities that are considered clinically insignificant or that are resolving with medical therapy

Should any one of the criteria above not be met, dosing of Sym015 must be delayed until the patient meets the above criteria. All per protocol assessments must be done.

7.1.4.3 Dose-Reduction for Sym015-Related Toxicities

Patients experiencing any of the following toxicities, assessed as possibly, probably, or related to Sym015, will have their dose reduced in accordance with the reduction schedule outlined in [Table 7](#).

1. Grade 3 non-hematologic toxicity regardless of duration, with the exceptions of:
 - a. Grade 3 nausea, vomiting, diarrhea, or fatigue lasting \leq 2 days with best supportive care
 - b. Grade 3 asymptomatic electrolyte abnormalities lasting \leq 3 days that are not considered clinically relevant by the Investigator and that resolve with medical therapy without requiring hospitalization
2. Any Grade 4 non-hematologic toxicity, with the exception of:
 - a. Grade 4 asymptomatic electrolyte abnormalities lasting \leq 3 days that are not considered clinically relevant by the Investigator and that resolve with medical therapy
3. Neutropenia that is:
 - a. Grade 3-4 febrile neutropenia
 - b. Grade 4 and sustained (i.e., ANC <500 per mm 3 , duration >5 days)
4. Thrombocytopenia that is:
 - a. Grade 3 with clinically significant hemorrhage
 - b. Grade 4 (platelets $<25,000$ per mm 3)
5. AST/ALT elevation $>3\times$ ULN with bilirubin elevation $>2\times$ ULN that cannot be explained by factors not related to study drug

Table 7 Sym015 Dose-Reduction Schedule

Allocated Dose	First Reduction	Second Reduction	Subsequent Reductions
6 mg/kg	3 mg/kg	1.5 mg/kg	Reduce by 50%
12 mg/kg	6 mg/kg	3 mg/kg	Reduce by 50%
18 mg/kg	12 mg/kg	6 mg/kg	Reduce by 50%
24 mg/kg	18 mg/kg	12 mg/kg	Reduce to 6 mg/kg, then by 50%

Note: In the event that an intermediate dose is explored in this study, dose-reductions in such cases will be to the next lower established tolerated dose level(s). If further dose-reductions are indicated, proceed as outlined above.

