3.4.2 Rationale for Recommended Phase 2 Dose

As of Amendment 4, following review of available safety (refer to Section 3.2.4.1) and PK data, the decision has been made to choose the following as the recommended Phase 2 dose (RP2D) on a Q2W schedule of Sym015 (referenced as the Q2W RP2D):

- Loading dose of 18 mg/kg infused over 1.5 hours on Cycle 1/Day 1 (C1/D1)
- Followed by Q2W maintenance doses of 12 mg/kg infused over 1 hour beginning on Cycle 1/Day 15 (C1/D15)

The rational for this choice is based upon preliminary PK data from the initial 6 mg/kg Q2W (N=3, 2-3 cycles) and 12 mg/kg Q2W (N=3, up to Cycle 2/Day 1) cohorts treated in the dose-escalation phase of this trial. These data were used to establish a population PK model.

The summary PK parameters for these data, based on non-compartmental analysis, are listed in [Table 1](#).

Table 1 Preliminary Sym015 Geometric Mean PK Parameters

Dose Q2W	N	AUC _{0-336h} 1 st dose (h x µg/mL)	C _{max} 1 st dose (µg/mL)	C _{trough} 2 nd dose (µg/mL)	C _{max} 3 rd dose (µg/mL)	t _½ 1 st dose (h)
6 mg/kg	3	19400	146	35.9	196	158
12 mg/kg	3	40000	294	119	396	213 (n=1)

Abbreviations: AUC, area under the concentration-time curve in a dosing interval; C_{max}, maximum concentration; C_{trough}, trough concentration; h, hour; N, number of patients; Q2W, dosing every second week; t_½, elimination half-life

The model was used to simulate average and 90% confidence intervals for Sym015 PK profiles for the 18+12 mg/kg Q2W regimen, and demonstrated that pre-dose serum concentrations, C_{trough}, are likely to be above 100 µg/mL for the vast majority of patients for all dose administrations. The serum concentration of 100 µg/mL has been defined as an approximate threshold for clinical efficacy. This has been deduced from the 750 mg Q2W dose regimen of another anti-MET monoclonal antibody, emibetuzumab, which has shown signs of efficacy in patients with *MET*-amplified tumors ([23,28](#)). It is assumed that similar serum concentrations of Sym015 and emibetuzumab will result in similar clinical efficacy because similar potencies between the two compounds have been observed in preclinical *in vitro* and *in vivo* studies (refer to Investigator's Brochure). *In vivo* studies also support that efficacy can be expected at concentrations above 100 µg/mL for both compounds.

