A safety monitoring committee (SMC) will be established and will include Investigator(s), Medical Monitor(s), and Sponsor's medical representatives. The SMC will review clinical and laboratory safety data regularly throughout the trial. The SMC will select the Q2W RP2D to be used in Part 2 based on safety data and available PK results.

Note: Effective with protocol version 5.0 (November 2016), following review of available safety and PK data, the decision has been made to choose the following as the Q2W RP2D of Sym015: Loading dose of 18 mg/kg infused over 1.5 hours on C1/D1, followed by Q2W maintenance doses of 12 mg/kg infused over 1 hour beginning on C1/D15. As the MTD has not yet been reached, dose-escalation will continue in Part 1 of the trial to 24 mg/kg.

During Part 2, three cohorts will receive Sym015 at the RP2D on a Q2W dosing schedule:

[figure not shown]
- Basket Cohort: A basket cohort of *KRAS* WT, advanced solid tumor malignancy patients with *MET*-amplification will be evaluated. Patients must be *MET*-targeting TKI-naïve; an exception will be a subset of approximately 6 patients entered who have received prior therapy with a *MET*-targeting TKI.

Note: Effective with protocol version 8.0 (December 2018), accrual to the Basket Cohort is suspended.

- NSCLC *MET*-Amplified Cohort: A cohort of advanced NSCLC patients with *MET*-amplification will be evaluated. Patients may have received prior therapy with *MET*-targeting and/or EGFR-targeting agents.
- NSCLC *MET*^{Ex14Del} Cohort: A cohort of advanced NSCLC patients with *MET*^{Ex14Del} will be evaluated. Tumors need not be *MET*-amplified, and patients may have received prior therapy with *MET*-targeting and/or EGFR-targeting agents.

The trial design is shown in [Figure 1](#).

Figure 1 Overall Trial Design

Abbreviations: EGFR, epidermal growth factor receptor; Dec, December; KRAS, KRAS proto-oncogene; MET, MET proto-oncogene; MET^{Ex14Del}, MET exon 14 skipping alteration; N, number of patients; NSCLC, non-small cell lung carcinoma; Q2W, dosing every second week; RP2D, recommended Phase 2 dose; TKI, tyrosine kinase inhibitor; WT, wild-type

Part 1 will be conducted in the United States (USA). Part 2 will be conducted in the USA and countries within the Asia Pacific and European regions. The number of investigational trial sites, hereafter called “trial sites”, expected to participate, will be approximately 2 to 3 in Part 1 and 15 to 27 in Part 2.

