Progression from a current dose level to the next will only proceed following evaluation of tolerability of the current dose level. Thus, dosing of the first patient at Dose Level 2 will commence only once all patients to be treated at Dose Level 1 have completed Cycle 1, and Dose Level 1 has been found to be tolerable. Similarly, dosing in Dose Level 3 will only commence once all patients to be treated at Dose Level 2 have completed Cycle 1, and Dose Level 2 has been found to be tolerable. The dose-escalation decision points are listed below:

- If no DLTs are encountered in any of the first 3 patients completing Cycle 1 within a dose level, dose-escalation may continue to the next level
- If 1 of 3 patients within a dose level experiences a DLT, 3 more patients will be enrolled at the same dose level. If no DLTs are encountered in the 3 additional patients, dose-escalation may continue to the next level
- If ≥ 2 patients within a dose level (of up to 6 patients) experience a DLT, then that dose will be considered to have exceeded the MTD and the dose level just below this dose level will be considered to be the MTD
- If no DLTs are encountered in any of the first 3 patients at Dose Level 4, 24 mg/kg will be considered the highest safe dose tested

The SMC will review safety data throughout the trial. During Part 1, the SMC will make decisions regarding the advisability of: continuing accrual to a particular dose cohort; dose-escalation and accrual of patients to a higher dose cohort; and the dose(s) to be used in Part 2 (i.e., Q2W RP2D to be evaluated).

Each patient enrolled will receive Sym015 at the allocated dose until treatment withdrawal, unless dose-reduction is necessary as specified in Section 7.1.4. There will be no intra-patient dose-escalation.

7.1.3.3 Part 2

During Part 2 of this trial, patients will receive the RP2D of Sym015 on a Q2W dosing schedule.

The SMC will continue to review safety data and assess the tolerability of Sym015 during Part 2 of the trial.

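### Table 7 does not say which row applies to a Part 2 patient with a reduction-triggering toxicity after the 18 mg/kg loading dose, and one of the two candidate rows returns the dose already scheduled

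*Protocol*

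**What the plan says.** Section 5.1 gives the recommended Phase 2 dose as "Loading dose of 18 mg/kg infused over 1.5 hours on C1/D1, followed by Q2W maintenance doses of 12 mg/kg", with maintenance starting on C1/D15. The synopsis and Section 3.4.2 give the same regimen. Section 7.1.3.3 applies it to the whole of Part 2: "During Part 2 of this trial, patients will receive the RP2D of Sym015 on a Q2W dosing schedule".

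Section 7.1.4.3 lists the related toxicities that call for a reduction and says that patients who have one "will have their dose reduced in accordance with the reduction schedule outlined in" Table 7. It does not restrict this to Part 1, and Section 5.3.4 refers to the same rules for treatment in general.

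The first column of Table 7 is headed "Allocated Dose". Its four rows are 6, 12, 18 and 24 mg/kg, the same as the four Part 1 dose levels in Section 7.1.3.2. The columns are allocated dose, first reduction, second reduction and subsequent reductions. Two rows could apply to a Part 2 patient:

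- "18 mg/kg 12 mg/kg 6 mg/kg Reduce by 50" percent
- "12 mg/kg 6 mg/kg 3 mg/kg Reduce by 50" percent

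The note under the table deals with an intermediate dose, should one be explored. Sections 5.3.2 and 7.1.4 say that the dose is documented and confirmed on the Screening and Allocation Form. They do not say which of the two Part 2 doses counts as the allocated one for Table 7.

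**The concern.** The table fits a patient who stays on one dose level, as in Part 1. A Part 2 patient has two planned levels, and the second is lower than the first by design. A reader at a site who looks up the dose the patient has just received (18 mg/kg) finds a first reduction to 12 mg/kg, which was due at the next infusion anyway. A reader who looks up the dose the patient is about to receive (12 mg/kg) finds 6 mg/kg.

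This is a mandatory safety rule, so it should not be open to a reading that leaves the planned dose unchanged. The situation is also foreseeable. Section 7.1.3.7 puts the highest risk of an infusion-related reaction at the first administration, which in Part 2 is the load. For a Grade 3 reaction, Table 6 offers discontinuation or continuation at a reduced dose, without naming the level. Section 7.1.3.4 records Grade 2 reactions in 2 of 3 Part 1 patients at 18 mg/kg, which led to the longer infusion.

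Reporting is affected too. Section 10.5.3 counts adverse events leading to dose reduction. A first reduction to 12 mg/kg after the load gives the same administered dose as no reduction, so that count cannot be interpreted without knowing which row was used.

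**Working it through.** This is a comparison of tabulated doses; no sample-size or error-rate calculation is involved.

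**Inputs**

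- Loading dose on C1/D1: 18 mg/kg (Section 3.4.2; Section 5.1)
- Next scheduled dose, from C1/D15: 12 mg/kg (same sections)
- First reduction, 18 mg/kg row: 12 mg/kg; second reduction 6 mg/kg (Table 7)
- First reduction, 12 mg/kg row: 6 mg/kg; second reduction 3 mg/kg (Table 7)

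**Case examined:** a listed, related toxicity after the C1/D1 load and before the C1/D15 infusion.

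**Formulas.** The protocol does not name a comparator, so both are shown.

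- Change against plan = (scheduled next dose − tabulated first reduction) / scheduled next dose
- Change against the load = (loading dose − tabulated first reduction) / loading dose

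| Row used | Next dose | Against plan (12 mg/kg) | Against load (18 mg/kg) |
|---|---|---|---|
| 18 mg/kg | 12 mg/kg | (12 − 12)/12 = 0% | (18 − 12)/18 = 33% lower |
| 12 mg/kg | 6 mg/kg | (12 − 6)/12 = 50% lower | (18 − 6)/18 = 67% lower |

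The same patient with the same event therefore receives 12 or 6 mg/kg, a twofold difference, depending on the row. Under the 18 mg/kg row only the second reduction (6 mg/kg) falls below planned dosing.

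**Does other text settle the row?**

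- The note under Table 7 concerns an intermediate dose. Section 7.1.3.2 uses that idea for a level between those listed. Both 18 and 12 mg/kg are listed levels, so the note does not reach this case.
- Section 7.1.3.3 (Part 2) contains no reduction rule.
- Section 7.1.4.2 says when dosing must wait, not what dose follows.
- Sections 5.3.2 and 7.1.4 point to the allocation form without saying whether 18, 12 or both are entered as the allocated dose.

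**Toxicity during maintenance.** From C1/D15 the dose being given is 12 mg/kg, so the 12 mg/kg row is the natural reading of the table. The protocol does not state this either.

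**The case against.** The best answer is that the two readings are not equally plausible. The governing sentence requires the dose to be reduced, and a reading that leaves the scheduled dose untouched fits it poorly; the 12 mg/kg row is there and does lower it. Moreover, 12 mg/kg is 33% below the dose at which the toxicity occurred, so calling it no reduction depends on comparing it with the plan. Both points stand as qualifications: the null result is conditional on the 18 mg/kg row and on the scheduled dose as comparator. Neither tells a site which row to use.

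There are other safeguards. Section 7.1.4.2 bars redosing until related events have improved, with stated exceptions. Table 6 stops treatment for a Grade 4 infusion-related reaction. Section 6.3.1 requires withdrawal when the investigator judges that an adverse event calls for it. The allocation form, which is not at hand, may settle the allocated dose, so it is not shown that sites do diverge. These points lessen the consequence, but none of the protocol text fixes the next dose for a patient who continues.

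A reader might also infer that reduction data become incomparable between sites. The document does not support that. Section 10.1 plans descriptive summaries without formal hypothesis testing, Section 10.5.3 presents safety by trial part, and no comparison between sites is planned. Section 7.1.3.1 records the total dose of every infusion and Section 12.1 has dose modifications entered in the CRF, so actual exposure is recoverable. What remains is narrower: the meaning of the count of events leading to dose reduction.

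**Conclusion.** The point holds in a limited form. Table 7 was not reconciled with the Part 2 regimen. For a qualifying related toxicity between the load and C1/D15, it gives either 12 mg/kg (0% against plan, 33% below the load) or 6 mg/kg (50% against plan, 67% below the load), and the protocol does not choose. Under the first reading a mandatory safety rule produces no change from planned dosing, which is more than a missing detail.

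Two stronger readings should be resisted. One is that Table 7 gives Part 2 patients no reduction at all; that follows only from the 18 mg/kg row set against scheduled maintenance. The other is that all 51-57 planned Part 2 patients are affected; that is the number on the regimen. Those directly affected are the patients with a qualifying toxicity after the load, and the document does not allow that number to be estimated. The revised Section 3.2.4.1 text in the Amendment 7 change table reports one Part 2 patient with two possibly related Grade 3 events, but not their timing relative to the load.

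No effect on the primary endpoint, confirmed objective response, is shown. The conclusion assumes that the allocation form does not itself identify the row.

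**What to change.** Reconcile Table 7 with the Part 2 regimen in the synopsis and Sections 3.4.2 and 5.1. The table, or a note to it, should state the reference dose for (a) a toxicity after the loading dose and before C1/D15 and (b) a toxicity during maintenance. The clinical team sets the levels; none is proposed here. The allocation form should use the same definition of allocated dose.

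Identify any Part 2 patient already reduced, with the timing of the event relative to the load and the row applied, so that the summary of adverse events leading to dose reduction (Sections 10.5.3 and 10.5.3.1) can be interpreted.

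The cost is one table entry or note in a protocol amendment and a short review of dosing records that Sections 7.1.3.1 and 12.1 already require. Sample size and the efficacy analyses are unchanged.

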6.3.1 Withdrawal from Treatment with Sym015

The patient must be withdrawn from treatment with Sym015 in the event of any of the following:

- A DLT considered by the Investigator to require treatment discontinuation. Refer to Section 9.5 for DLT definition (dose-escalation cohorts only)
- Occurrence of an AE considered by the Investigator to require treatment discontinuation
- Basket Cohort ONLY: Results from archival tumor tissue or a tumor biopsy submitted to confirm *MET*-amplification status that do not meet study eligibility criteria.

Note: Such patients may remain on study if there is evidence of an OR, SD, or other clinical benefit, but will not be included in the Evaluable for Response Population.

- PD, verified by CT/MRI according to RECIST v1.1
- Treatment failure not meeting the criteria for PD, but considered by the Investigator to require treatment discontinuation
- Requirement for a significant surgical procedure

Note: Patients requiring a minor surgical procedure (e.g., port placement, skin abscess drainage) may continue at the Investigator's discretion following discussion with the Sponsor or designee. A brief interruption in therapy may be considered

- An intercurrent illness which, in the opinion of the Investigator, would prevent completion of trial-related evaluations
- Use of prohibited concomitant medication, as defined in Section [7.5.2](#)
- Pregnancy
- Significant deviation from the eligibility criteria may require discontinuation after discussion with the Sponsor
- Noncompliance with trial procedures may require discontinuation after discussion with the Sponsor
- Patient withdrawal of consent and election to discontinue treatment. (Patients may leave the trial at any time for any reason if they wish to do so, without any consequences)
- Termination of the trial by the Sponsor
- Patients who meet Hy's Law criteria that cannot be explained by factors not related to Sym015.

Note: Patients meeting all three of the following are considered to have met Hy's Law criteria:

- The drug causes hepatocellular injury, generally shown by a higher incidence of 3-fold or greater elevations above ULN of ALT or AST
- Among trial subjects showing such aminotransferase elevations, often much greater than 3xULN, one or more show elevation of serum total bilirubin to ≥ 2 xULN, without initial findings of cholestasis (elevated serum alkaline phosphatase [ALP]).

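### Unexplained liver injury meeting Hy's Law falls under both mandatory dose reduction (7.1.4.3, item 5) and mandatory withdrawal (6.3.1), and neither rule is given precedence

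*Protocol*

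**What the plan says.** Section 7.1.4.3 covers toxicities assessed as possibly, probably or definitely related to Sym015. Patients with a listed toxicity "will have their dose reduced in accordance with the reduction schedule outlined in" Table 7. Item 5 is AST/ALT above 3xULN together with bilirubin above 2xULN "that cannot be explained by factors not related to study drug". It sets no condition on ALP and makes no exception for Hy's Law.

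Section 6.3.1 opens its list with "The patient must be withdrawn from treatment with Sym015 in the event of any of the following". One entry is "Patients who meet Hy's Law criteria that cannot be explained by factors not related to Sym015". A Note then gives three criteria, all of which must be met:

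- First, Sym015 is the cause of liver-cell damage. The Note adds that this is "generally shown by a higher incidence of 3-fold or greater elevations above ULN of ALT or AST", which it offers as the usual evidence.
- Second, on bilirubin, the Note states: "Among trial subjects showing such aminotransferase elevations, often much greater than 3xULN, one or more show elevation of serum total bilirubin". The level required is at least 2xULN, with ALP not raised at the outset.
- Third, nothing else accounts for the findings.

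The same section also allows withdrawal on judgment: "Occurrence of an AE considered by the Investigator to require treatment discontinuation". Section 7.1.4.2 sets the conditions for giving the next dose. If any is not met, "dosing of Sym015 must be delayed until the patient meets the above criteria".

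**The concern.** Two mandatory instructions appear to apply to the same patient and to order opposite actions: give less drug, or give no more drug. The event is possible drug-induced liver injury with raised bilirubin, where the difference matters for the patient.

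If item 5 is followed, treatment can resume at a lower dose where 6.3.1 demands a stop. In practice, a stop written as mandatory becomes discretionary. With 15 to 27 sites planned for Part 2, the same event could be handled differently from site to site. It would then be counted in different tables under Section 10.5.3.1: among AEs leading to withdrawal at one site, and among AEs leading to interruption or dose reduction at another.

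**Working it through.** There is no figure to reproduce. The check compares the two rules and then follows the consequence of each.

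**1. Can the Hy's Law rule in 6.3.1 be applied to one patient?** Yes.

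- The main clause of the first criterion is that the drug causes hepatocellular injury. The incidence phrase says only how this is generally shown. For a single patient, it is the kind of causality judgment that Section 9.2.4 already asks of the Investigator for every AE.
- The second criterion needs one or more subjects with the aminotransferase elevation to have raised bilirubin, so the first such patient satisfies it.
- The third criterion, and the no-cholestasis clause in the second, are patient-level as they stand.
- Both the bullet and the Note's lead-in speak of patients who meet the criteria.

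The wording is awkward because it borrows drug-level and trial-level language, but the rule works.

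**2. Triggers and actions side by side.**

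| | 7.1.4.3 item 5 | 6.3.1 Hy's Law |
|---|---|---|
| AST/ALT | >3xULN | 3-fold ULN or greater |
| Total bilirubin | >2xULN | ≥2xULN |
| ALP | no condition | not initially raised |
| Other cause | none outside study drug | none found |
| Relatedness | possibly, probably or related | drug causes the injury |
| Action | reduce dose per Table 7 | withdraw from Sym015 |

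**3. Overlap.**

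- Above both limits, unexplained, ALP not initially raised: both rules apply.
- Above both limits, unexplained, ALP initially raised: only item 5 applies.
- AST/ALT exactly 3xULN or bilirubin exactly 2xULN, with the other at or above its limit and the remaining Hy's Law conditions met: only 6.3.1 applies.

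Apart from exact equality, every Hy's Law case under 6.3.1 that is assessed as related is also an item 5 case.

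**4. Is precedence stated?** No. Section 6.3.1 refers to 9.5 and 7.5.2 but not to 7.1.4.3, and 7.1.4.3 does not refer to 6.3.1. Section 5.3.4 introduces dose reduction by pointing to 7.1.4 and is silent on Hy's Law.

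**5. If a site follows item 5, do the re-dosing conditions in 7.1.4.2 prevent treatment?** Not reliably.

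- The bar on dosing while an AE meets DLT criteria applies only in the DLT observation period. That period is Cycle 1 (Section 9.5.2), and DLTs apply to Part 1 only (Section 9.5).
- A related AE must otherwise have improved to Grade 1 or less, returned to baseline or resolved. Asymptomatic laboratory abnormalities that are resolving with medical therapy are exempt.

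A Part 2 patient without symptoms whose liver values are improving under treatment could therefore be dosed again before returning to Grade 1 or baseline. Part 2 accounts for 51 to 57 of the 63 to 72 planned patients (51/63 = 0.81; 57/72 = 0.79), about four-fifths of the trial.

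**The case against.** The best reply is that the rules can be ordered without an edit. A withdrawn patient has no later dose to reduce, so complying with 6.3.1 leaves 7.1.4.3 nothing to act on. Item 5 is the broader rule and keeps its own content for cases with initial cholestasis, while 6.3.1 governs the narrower Hy's Law group. Section 5.3.4 describes dose reduction in permissive terms. Several safeguards also stand behind the text: laboratory results must be assessed before each infusion (8.2.9), the Medical Monitor evaluates abnormal values (12.2), and the Investigator can withdraw a patient for any AE and uses clinical judgment before each dose.

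Much of this stands. Withdrawal first is the natural and safer reading, and nothing compels re-dosing. The descriptive AE tables carry no hypothesis test, so moving an event between them biases no efficacy estimate.

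The reply still does not remove the conflict. The order is inferred, because no sentence states it and item 5 draws no line at ALP. The safeguards are matters of judgment, whereas 6.3.1 is written so that judgment is not needed once the criteria are met.

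**Conclusion.** The inconsistency is real and should be corrected. For related, otherwise unexplained elevations above both limits without initial ALP elevation, the protocol orders both dose reduction and withdrawal and does not say which prevails. This rests on the current text of the two sections. It assumes that an Investigator who judges the event related and finds no other cause would also accept that the drug caused the injury.

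Two stronger readings are tempting, and the document supports neither.

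- A reader might infer that the Hy's Law Note cannot be checked in one patient, so that item 5 is the only rule that operates. Step 1 of the working shows otherwise: the Note is clumsy but usable.
- A reader might set the liver-function limits in Section 6.2 against item 5 and infer that the collision will be common. Those limits do not measure this, because item 5 also needs relatedness and the absence of a non-drug explanation, and liver metastases are one such candidate explanation. The document gives no rate.

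The primary endpoint, sample size and efficacy analyses are untouched. What is at stake is consistent handling and reporting of a potentially serious liver event.

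**What to change.** Make three edits at the next amendment.

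1. In 7.1.4.3, delete item 5, or limit it to cases that do not meet Hy's Law, for example those with raised ALP at onset.
2. In the same section, add: *Patients meeting Hy's Law criteria (Section 6.3.1) are not eligible for dose reduction; Sym015 is permanently discontinued.* Place it so that it governs the whole list. Items 1 and 2 also order reduction for related Grade 3 and Grade 4 non-hematologic toxicity, so a severe liver event could otherwise still enter there even with item 5 deleted.
3. In 6.3.1, replace the Note with patient-level criteria: in the same patient, ALT or AST at least 3xULN and total bilirubin at least 2xULN, no initial ALP elevation, and no other cause found.

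The cost is a few lines of text in two sections. No assessment, sample size or analysis changes.
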